# 2.4 Clinical Studies with HF10

#### **Completed Phase I Studies of HF10 in Japan**

HF10 was studied previously in patients with breast cancer  $(N=6)^{50}$ , head and neck cancer  $(N=3)^{51}$ , and unresectable pancreatic cancer  $(N=8)^{52}$  in three investigatorinitiated open-label studies conducted in Japan. The only adverse event reported was low-grade fever in two of the three treated patients with head and neck cancer. This adverse event is consistent with adverse events reported previously in other clinical studies of oncolytic viruses (e.g. flu-like symptoms such as low grade fever, chills, fatigue, nausea/vomiting, headache, diarrhea, and hypotension).

#### Phase I Study of HF10 in Patients with Refractory Head and Neck Cancer or Solid Tumors with Cutaneous and/or Superficial Lesion in the US (Protocol No. M06-10083, under BB-IND 13342)

This was an open label, non-randomized, multicenter, two-stage, dose escalation Phase I study evaluating single and repeated intratumoral injections of the oncolytic virus, HF10, in patients with refractory head and neck cancer, or solid tumors with cutaneous and/or superficial lesions (e.g., squamous cell carcinoma of the skin, carcinoma of the breast, and malignant melanoma).

Stage 1 of the study investigated dose escalation of a single intratumoral injection of HF10 over the following dose levels:  $1 \times 10^5$  TCID50,  $3 \times 10^5$  TCID50,  $1 \times 10^6$  TCID50, and  $1 \times 10^7$  TCID50. In Stage 1, 3 patients were to be enrolled per single dose cohort. Within each single dose cohort, accrual would temporarily be suspended after the first patient was entered and the patient was followed for safety and for viral distribution and elimination. In the single dose cohorts, after the first patient in a cohort showed no significant increase of virus DNA in comparison to baseline in two consecutive weekly samples of each specimen (whole blood, saliva, and urine), safety considerations permitting, entry of two additional patients would occur concurrently. Escalation to the next dose level required confirmation of no significant change of virus DNA, as described for the first patient in each cohort. All patients in a cohort completed the first cycle of treatment (with a 28-day safety observation period), before escalation to the next cohort was initiated. The patients in Stage 1 were required to be seropositive for HSV-1. Stage 1 was completed.

Stage 2 evaluated repeated intratumoral injections of HF10 at dose levels of  $1 \times 10^6$  TCID50/dose and  $1 \times 10^7$  TCID50/dose. Three patients were enrolled in each of the repeated dose cohorts.

In Stage 2, the first patient treated in each repeated dose cohort was required to be seropositive for HSV-1. Then, if no safety issue had occurred as a result of HF10 treatment of the first patient in a cohort, the cohort was to be opened to enrollment of HSV-1 seropositive and seronegative patients. Accrual on the cohort was temporarily suspended for seronegative patients only, i.e., after enrollment of the first seronegative patient in a cohort, a second seronegative patient could not be enrolled in the cohort until after the first seronegative patient completed the safety observation period for 2 cycles of treatment. If all of three patients were seropositive, one seronegative patient could additionally be enrolled.

Twenty-eight patients were enrolled in the study and a total of 26 patients were treated in the study (15 patients in Stage 1 and 11 patients in Stage 2). Two patients were not evaluable for safety because they were not treated with HF10; one withdrew consent before HF10 treatment and one was not treated with HF10 due to hospitalization for pneumonia. Another patient, enrolled in Stage 2 (repeated HF10 administration portion of the study), was not evaluable for dose limiting toxicities (DLTs) per protocol because the patient received only one HF10 injection; Stage 2 patients were required to receive two HF10 injections to be considered evaluable for DLTs.

Twenty-four (92.3%) of the 26 patients treated in this study experienced adverse events.

Treatment-emergent adverse events (TEAEs) were reported for  $\geq 20\%$  of patients in the following system organ classes, in descending order: general disorders and administration site condition (13 patients; 50.0%), gastrointestinal disorders (8;

Protocol name: Phase II Neoadjuvant trial of Nivolumab in Combination with HF10 Oncolytic Viral Therapy in Resectable Stage IIIB, IIIc, IVM1a Melanoma (Neo-NivoHF10) Version Date: 22JUL2019 Principal Investigator: [name]

30.8%), and metabolism and nutrition disorders (8; 30.8%). The most frequently reported TEAEs were chills, fatigue, and nausea, each reported for 3 patients (11.5%).

Nine patients (34.6%) reported HF10-related TEAEs. The most frequent related TEAEs were chills, experienced by 3 patients (11.5%), and fatigue, which was reported for 2 patients (7.7%). Regarding the repeat dosing cohorts, fewer patients (33.3%) in the lower dose cohort (1 x 10^6 TCID50/mL/dose) experienced HF10-related TEAEs compared to patients (50.0%) in the 1 x 10^7 TCID50/mL/dose cohort, suggesting a dose-response. It is notable that the frequent HF10-related TEAEs (chills and fatigue) were generally mild and are symptoms reported commonly and easily managed in viral infections and treatment with other oncolytic viruses. All other HF10-related TEAEs were each reported for one patient. Overall, 8 patients (30.8%) reported severe ( $\geq$  Grade 3) TEAEs. No patients reported an event that was both HF10-related and Grade 3 or greater in severity. No HF10-related allergic events were reported. Also, there were no differences in toxicity between patients who were HSV-1-positive and HSV-1-negative at enrollment. No HF10-related serious adverse events were reported in this study.

Viral clearance was investigated following intratumoral injection of HF10. Viral clearance was assessed in blood, saliva, and urine samples by quantitative polymerase chain reaction (qPCR). Patients showed rapid clearance of virus in blood, saliva, and urine. In both stages of the study, HF10 DNA was not detected in any of the biological samples in the majority of patients. For the few patients in whom HF10 DNA was detected, it was almost exclusively restricted to saliva samples and was only transiently detected in samples. Two patients in Stage 1 had transient virus detection in saliva only. In Stage 2, 6 patients had transient virus detection in saliva only. Two patients in Stage 2 had transient virus detection in blood, and one of these patients also had transient virus detection in urine.

All 26 patients are off-study. The reasons for off-study are as follows: thirteen (50.0%) patients total, including 7 (46.7%) patients in Stage 1 and 6 (54.5%) patients in Stage 2, were off-study due to progressive disease per RECIST evaluation. Ten (38.5%) patients completed the study per protocol (including 5 patients (33.3%) in Stage 1 and 5 patients (45.5%) in Stage 2 [3 patients in the 1 x 10^6 TCID50/mL cohort and 2 in the 1 x 10^7 TCID50/mL cohort]). Two (7.7%) patients were off-study due to unrelated death; both patients were treated in Stage 1. One (3.8%) patient in Stage 1 was removed from the study due to symptomatic deterioration.

#### Clinical Studies with HF10 + Ipilimumab in unresectable melanoma

# Phase 2 multicenter trial to evaluate efficacy and safety of HF10 oncolytic virus immunotherapy and ipilimumab in patients with unresectable stage IIIB-IV melanoma in the US (Protocol T14-10682, IND No 13,342)

An ongoing phase 2 trial of HF10 and ipilimumab in unresectable metastatic melanoma patients is assessing whether the antitumor effect of HF10 is enhanced by concurrent ipilimumab treatment. Ipilimumab naïve adults with Stage IIIB, IIIC or IV unresectable melanoma with measurable non-visceral lesion(s) received HF10

injections into single or multiple tumors  $(1 \times 10^7 \text{ TCID}_{50}/\text{mL}, \text{ up to } 5 \text{mL/dose}); 4$ injections every week; then up to 15 injections every 3 weeks. Ipilimumab infusions (3 mg/kg) were given every 3 weeks for 4 doses. Tumor responses were assessed at 12, 18, 24, 36, and 48 wks. Best Overall Response Rate (BORR) was determined at 24 wks. Of 46 pts treated, 20% were stage IIIB, 43% stage IIIC, and 37% stage IV. Most HF10-related AEs were  $\leq$  Grade 2, similar to HF10 monotherapy. No DLTs were reported; 3 Grade 4 AEs reported, all not treatment related. 30.4% had Grade 3 AEs. HF10-related Grade 3 AEs (n=3) were left groin pain, thromboembolic event and lymphedema, hypoglycemia, and diarrhea. Twenty-one (46%) patients had received at least 1 prior therapy for metastatic melanoma. Of 43 efficacy evaluable patients, preliminary BORR at 24 weeks per irRC was 41.8% (11.6% CR, 30.2% PR), disease stability rate 67.4% (25.6% SD). Eight responders (53%) were Stage IV. Overall study BORR, including those after 24 weeks, by irRC was 47.7% (15.9% CR, 31.8% PR), disease stability was 65.9% (18.2% SD). In summary, HF10 in combination with ipilimumab treatment does not appear to exacerbate ipilimumab toxicity, is safe, well tolerated and has both local and systemic antitumor activity. The efficacy appears greater than that seen with ipilimumab monotherapy. Since the clinical trial is on-going, the final results of the trial are still pending.

# Clinical Studies with Nivolumab

One Phase 1 study (CA209003) has contributed much to the clinical experience with nivolumab monotherapy in subjects with melanoma and other solid malignancies. CA209003 is an ongoing Phase 1 open label, multiple dose escalation study in 304 subjects with select previously treated advanced solid tumors, including melanoma, renal cell carcinoma (RCC), non-small cell lung cancer (NSCLC), colorectal cancer, and hormone-refractory prostate cancer. Subjects received nivolumab at doses of 0.1, 0.3, 1, 3 or 10 mg/kg intravenously every 2 weeks, up to a maximum of 2 years of total therapy. As of 03-Jul-2012, a total of 107 melanoma subjects were treated with nivolumab in the dose range of 0.1 - 10 mg/kg.

No maximal tolerated dose was identified in CA209003. The incidence, severity and relationship of AEs were generally similar across dose levels and tumor types. Nivolumab related AEs of any grade occurred in 72.4% of subjects. The most frequent nivolumab related AEs occurring in 5% of subjects included: fatigue (25.7%), rash (13.5%), diarrhea (11.8%), pruritus (10.2%), nausea (7.9%), decreased appetite (7.9%), hemoglobin decreased (5.9%) and pyrexia (5.3%). The majority of events were low grade, with Grade 3 - 4 drug related AEs observed in 14.8% of subjects. The most common Grade 3 - 4 drug-related AEs occurring in 1% of subjects were: fatigue (1.6%), lymphopenia (1.3%), abdominal pain (1%), diarrhea (1%), hypophosphatemia.

# **3** POTENTIAL RISKS AND BENEFITS

# 3.1 HF10

Potential risks of investigational intratumoral injections include the following reported adverse events:

Occurring in more than 10% of subjects - chills

Occurring in 1%-10% of subjects - injection site disorders, fatigue, malaise, pyrexia, nausea, dehydration, pruritus, and/or hypotension

One patient with anal and scrotal tumors injected with HF10 experienced swelling in the genital area, skin breakage and scab formation in the area on/near the scrotum.

The results of previous and ongoing clinical trials of HF10 in Japan, and the Phase I clinical trial of HF10 conducted under BB-IND 13,342, suggest that HF10 is safe and tolerable. Few HF10- related adverse events have been reported in any of the trials and are similar across the trials. They include: flu-like symptoms such as fever, chills, fatigue, nausea/vomiting, and hypotension. Such events are consistent both with symptoms of viral infections and adverse events reported in trials of other investigational oncolytic viruses. No HF10-related serious adverse events have been reported in these trials.

In the event that HF10-treated patients experience unexpected viral toxicity, patients may be treated by the anti-herpes drugs acyclovir, famciclovir, or valacyclovir, to which HF10 is sensitive.

The Investigator Brochure may be updated during the course of this study with additional risks and benefits. Please see the current Investigator Brochure for further details about the potential risks and benefits associated with this study.

Treatment with HF10 may offer potential benefits. Preliminary evidence suggests that intratumoral injection with HF10 may result in an antitumor response.

# 3.2 Nivolumab

Overall, the safety profile of nivolumab monotherapy is manageable and generally consistent across completed and ongoing clinical trials with no MTD reached at any dose tested up to 10 mg/kg. There was no pattern in the incidence, severity, or causality of AEs to nivolumab dose level. Most AEs were low-grade (Grade 1-2) with relatively few drug-related high-grade (Grade 3-4) AEs. The most common adverse events ( $\geq 20\%$ ) in patients with melanoma were fatigue, rash, musculoskeletal pain, pruritus, diarrhea and nausea. The safety profile of nivolumab combination therapy varies with the agent combined with nivolumab, but is generally consistent with the safety profiles observed with either agent alone and, in some cases, both frequency and severity of AEs were greater than that observed with either agent alone.

The Investigator Brochure may be updated during the course of this study with additional risks and benefits. Please see the current Investigator Brochure for further details about the potential risks and benefits associated with this study.

Treatment with nivolumab offers patients potential benefits. In a significant proportion of nivolumab-treated patients, durable tumor responses were achieved, as well as a significant increase in overall survival.

# 4 STUDY DESIGN

#### 4.1 **Description**

This is a single-arm, open label, Phase II study evaluating the safety and efficacy of neoadjuvant Nivolumab and HF10 in resectable stage IIIB, IIIC, and IVM1a melanoma.

# 4.2 Number of Patients

The total number of subjects for all sites is initially planned as 20 patients. The primary endpoint of pathologic response rate, including pCR, is expected to be seen in 20% of patients, hence 4 of the planned 20 patients are expected to have a pathologic response including pCR. Only patients who receive the combination neo-adjuvant treatment, nivolumab and HF10, and have a surgical resection according to the study calendar will be considered evaluable. Patients who discontinue the study before surgery then will be considered non-evaluable and will be replaced per principal investigator discretion.

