# 6.1.2 Surgery

Surgery will be performed within 28 days of completing neo-adjuvant therapy with nivolumab and HF10. Patients who cannot proceed to surgery will not be evaluable and will be replaced. Patients may be allowed to remain on study treatment at the discretion of the principal investigator.

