6. Biopsies are mandatory at day 0 and surgery. Biopsies are optional at day 42 and progression. See section 13.1 for details about the collection.

7. Adverse events will be followed until resolution while the patient remains on treatment. Events will be followed for 90 post treatment for SAEs and events thought to be related to the study medication will be followed until resolution or stabilization of the adverse event, or until the patient starts a new treatment regimen.

8. Surgery should occur no later than 28 days after D84.

9. Adjuvant nivolumab should be initiated within 90 days after definitive surgery.

10. EOT visit should occur 28 days (+-14 days) after the completion of therapy.

11. Follow-up should occur every three months (+-or 14 days) for 1 years post EOT visit.

12. Surgery will reset the scan schedule and should occur approximately every 12 weeks after surgery as standard of care.

13. Pathology at surgery will be used to determine pathological response.

14. Collection of blood samples for correlatives is optional and will be collected prior to HF10 injection during the neo-adjuvant (days 0,7, 14, 21, 28, 42, 56, 70, 84) and prior to nivolumab infusion during the adjuvant nivolumab administration.

15. Men and women of childbearing potential must agree to use adequate contraception from the time of consent through 7 months after nivolumab study treatment (neoadjuvant and adjuvant). A pregnancy test will be conducted w/in 72 hours prior to beginning adjuvant nivolumab.

16. Next generation sequeencing is required at screening as per standard of care. Testing will include, but is not limited to BRAF mutational analysis.

17. Thyroid Tests will include TSH and free T4. In the event of hypo/hyper thyroidism, appropriate support will be provided in accordance with institutional guidelines.

18. Lesion photography should be completed at each time point AND when a new lesion is identified.

19. irRC and RECIST should be done prior to surgery. Only RECIST will be used as clinical response criteria and used to make treatment decisions

Protocol name: Phase II Neoadjuvant trial of Nivolumab in Combination with HF10 Oncolytic Viral Therapy in Resectable Stage IIIB, IIIc, IVM1a Melanoma (Neo-NivoHF10) Version Date: 22JUL2019 Principal Investigator: [name]

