# 9 CRITERIA FOR EVALUATION AND ENDPOINT

## 9.1 **Pathological response**

The primary objective of this study will be to identify the pathologic response rate at surgery, including complete response, after 12 weeks of neoadjuvant treatment with nivolumab and HF10. Pathologic response rate will be defined based on the quantity of residual viable tumor in the surgical resection specimen at the time of definitive surgery. A percent viable tumor will be assessed semi-quantitatively in the pre treatment biopsy, on study biopsy at day 42 and the definitive surgical resection specimen by estimating the proportion of residual tumor in relation to the total tumor area and reported as percentage viability (Ribero et al 2007) as per institutional practice. A pathologic complete response will be defined as no viable residual melanoma cells in the surgical specimen. A major pathologic response will be defined as <50% viable tumor cells. A minor pathologic response will be defined as 50% or greater viable tumor cells, including specimens that have 100% viability at surgery. Pathologic response rate (pRR) will be defined as frequency of either pCR or a pathologic major response. This will be compared to the viablity values of the tumor at baseline. Biopsies will be required at Day 0 and at surgery to perform this analysis. A patient must complete the neoadjuvant phase of the trial and complete surgery to be considered evaluable for pathological response.

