## 9.8 Complete Surgical Resection

Patients will be assessed at surgery to determine if complete surgical resection was achievable after neo-adjuvant treatment with nivolumab and HF10. Completeness of surgical resection will be defined by standard definitions as follows: R0 indicates all gross clinical disease resected with microscopic pathologic negative margins; R1 indicates all gross clinical disease; R2 indicates inability to completely excise all clinical disease (i.e. gross residual tumor unable to be removed at surgery).

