# **10 STATISTICAL CONSIDERATIONS**

The primary endpoint of pathologic response including pCR is expected to be seen in 30% of patients, hence 6 of the planned 20 patients are expected to have a pathologic response, including pCR.

Pathological response will be determined by assessing the tumor viability at baseline and at surgery. Samples will be scored as a percentage viability (0-100%). A pathologic complete response (pCR) will be defined as no viable residual melanoma cells in the surgical specimen. A major pathologic response will be defined as <50% viable tumor cells. A minor pathologic response will be defined as 50% or greater viable tumor cells, including specimens that have 100% viability at surgery. Pathologic response rate (pRR) will be defined as frequency of either pCR or a major pathologic response. Analysis will also be performed of baseline tumor biopsies and on treatment biopsies if available for comparisons with the surgical resection specimen.

The null hypothesis is that the pathologic response rate for patients receiving the treatment is 5% or less. The alternative hypothesis is that the pathologic response rate is 30%. With 20 evaluable patients there will be 59% power using an exact binomial test at the one-side 0.05 significance level if the true response rate is 20%, and 89% power at one-sided alpha = 0.05 if the true response rate is 30%. Four or more pathologic responses in up to 20 patients will be sufficient to reject the null hypothesis. In additional to the statistical test, a 95% exact binomial confidence interval for the pathologic response rate will be calculated.

Kaplan-Meier methods and associated confidence intervals will be used to analyze RFS and OS. All subjects assessed for relapse will contribute to this analysis.

The statistical analysis of the safety data will be descriptive and tabular in nature.

The statistical analysis of pathologic and correlative exploratory endpoints will be descriptive. No hypothesis tests will be performed for exploratory endpoints.

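### The primary pathologic response rate leaves out and replaces treated patients who do not reach surgery, so the estimate and its interval are biased upward for the treated population if such losses occur

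*Combined protocol and SAP*

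**What the plan says.** The design has no comparator: "This is a single-arm, open label, Phase II study evaluating the safety and efficacy of neoadjuvant Nivolumab and HF10".

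Three sections set the denominator of the primary rate.

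- Section 4.2: only patients who receive both agents and "have a surgical resection according to the study calendar will be considered evaluable". It continues: "Patients who discontinue the study before surgery then will be considered non-evaluable and will be replaced per principal investigator discretion".
- Section 6.1.2: "Patients who cannot proceed to surgery will not be evaluable and will be replaced".
- Section 9.1: "A patient must complete the neoadjuvant phase of the trial and complete surgery to be considered evaluable for pathological response".

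The calendar in section 8 fixes the window: "Surgery should occur no later than 28 days after D84".

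Section 10 sizes the test on that set ("With 20 evaluable patients there will be 59% power" at a true rate of 20%, and 89% at 30%) and rejects with four or more responses. Its null of 5% or less refers to patients given the treatment. It plans no all-treated rate, no rule for patients without a specimen and no sensitivity analysis.

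On resection, section 9.8 says: "Patients will be assessed at surgery to determine if complete surgical resection was achievable after neo-adjuvant treatment with nivolumab and HF10". It states no denominator.

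**The concern.** Every patient must have resectable disease at entry (section 5.1.2), so failing to reach surgery happens after treatment has begun and may be a result of it. Section 6.5 requires withdrawal for death and for serious local events from the injections. Section 7.1.1 lists toxicities that end nivolumab permanently, and section 7.1.2 withdraws patients who cannot tolerate reduced-dose HF10. Disease that makes surgery impossible falls under section 6.1.2. None of these losses is exempted from the evaluability rule. In a single arm, nothing offsets the resulting selection.

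The rules also differ among themselves. Evaluability rests on receiving the combination in section 4.2 and on completing the neoadjuvant phase in section 9.1. Replacement is discretionary in section 4.2 and unconditional in section 6.1.2. A patient who stops one agent early and is then operated on could be classified either way, in an open-label trial whose decision turns on four responses.

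At stake are the reported response rate and its interval, which are the trial's main results. The go/no-go test is affected much less.

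**Working it through.** **Inputs.** From section 10: 20 evaluable patients, null rate 5%, alternatives 20% and 30%, exact one-sided test at 0.05, rejection at 4 or more responses, 95% exact interval. The pre-surgery loss fraction d is not in the documents; it is assumed here. Patients lost before surgery are taken as non-responders.

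**1. The plan's own figures.** With X ~ Bin(20, p):

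- P(X ≥ 4 | 0.05) = 0.0159, the attained level. A cutoff of 3 would give 0.0755, so 4 is correct.
- P(X ≥ 4 | 0.20) = 0.589 and P(X ≥ 4 | 0.30) = 0.893. The stated 59% and 89% reproduce for the evaluable set.

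**2. Effect on the rate.** All-treated rate = evaluable rate × (1 − d).

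- d = 0: 30%, no bias.
- d = 10%: 0.30 × 0.90 = 27%.
- d = 20%: 0.30 × 0.80 = 24%.

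**3. Effect on the interval** (Clopper-Pearson, two-sided 95%).

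| Responses | 20 evaluable | 2 replaced (22 treated) | 5 replaced (25 treated) |
|---|---|---|---|
| 6 | 30.0% (11.9–54.3) | 27.3% (10.7–50.2) | 24.0% (9.4–45.1) |
| 4 | 20.0% (5.7–43.7) | 18.2% (5.2–40.3) | 16.0% (4.5–36.1) |

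**4. Effect on the test.** If the all-treated rate is 5% and every responder reaches surgery, the evaluable rate is 0.05/(1 − d), and the chance of at least 4 of 20 is:

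| d | Evaluable rate | P(X ≥ 4) |
|---|---|---|
| 0 | 5.00% | 1.6% |
| 10% | 5.56% | 2.3% |
| 20% | 6.25% | 3.3% |
| 30% | 7.14% | 5.0% |

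**5. Is 4 still a valid cutoff over all treated?** P(X ≥ 4 | n, 0.05) is 0.026 at n = 23, 0.034 at 25, 0.049 at 28 and 0.055 at 29. The exact cutoff is therefore 4 for 17 to 28 treated and 5 for 29 to 40. With 20 evaluable patients, the decision is the same on either denominator for up to 8 replacements.

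**6. Power of the all-treated analysis** (30% response among those operated on, 20% loss, so 24% overall).

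- Replacement until 20 are operated on, 20/0.8 = 25 treated: P(X ≥ 4 | 25, 0.24) = 0.883.
- Stopping at 20 treated: P(X ≥ 4 | 20, 0.24) = 0.743.

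**The case against.** The best defence is that pathologic response needs a surgical specimen, that the evaluable set is openly prespecified, and that the power figures are right for it. That is true, and an evaluable-only rate is a legitimate supportive result. It does not answer a hypothesis about everyone treated.

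Several stronger readings are tempting, and the documents do not support them.

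- *The test loses its error control.* The 4-of-20 rule attains 1.6% against a stated 5%, and that slack absorbs losses up to about 30%.
- *Three replacements overturn a result of 4 responses.* The two-sided 95% lower limit for 4/23 is 4.95%, just under the null, but that limit corresponds to a one-sided 0.025 test. At the plan's one-sided 0.05, 4/23 gives p = 0.026 and 4/25 gives p = 0.034; both reject.
- *Every lost patient is a treatment failure.* Consent withdrawal and loss to follow-up need not be. Nor need off-calendar surgery: section 7.1.1 allows nivolumab to be withheld for up to 12 weeks with HF10 delayed alongside, and such a patient may have responded. Progression is not a listed withdrawal reason in section 6.5; a patient who progresses but is operated on within the rules stays in the denominator.
- *Lost resectability never counts against the resection rate.* Section 9.8 classes gross disease that cannot be removed at surgery as R2, so failure found at operation does count. Only patients never taken to surgery are unaddressed.

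**Conclusion.** The point holds for the estimate and its interval. As written, the plan drops and replaces treated patients who do not reach surgery, including those lost to toxicity, death or disease that prevents surgery, and its denominator does not match the population named in its own null hypothesis. Under assumed losses of 10% and 20%, a reported 30% corresponds to 27% and 24% of all treated. The size depends wholly on a loss rate that the documents do not give and on counting lost patients as non-responders, which is a conservative convention. With no losses the bias is zero.

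The effect on the test is small: 3.3% false-positive probability at 20% loss, with the 4-response cutoff valid up to 28 treated. The inconsistent evaluability and replacement wording needs reconciling whatever the loss rate.

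**What to change.** In sections 4.2, 6.1.2, 9.1 and 10:

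1. Define the primary analysis set as all patients who receive at least one dose of nivolumab or HF10.
2. Count patients without an assessable surgical specimen as non-responders. Count any assessable specimen as scored, including one from off-calendar surgery.
3. Use the exact critical value for the number treated: 4 for 17 to 28, 5 for 29 to 40.
4. Keep the evaluable-only rate as supportive, and report the reasons for no surgery.
5. Replacement may continue, but replaced patients stay in the denominator.
6. Use one evaluability definition (4.2 against 9.1) and one replacement rule (4.2 against 6.1.2).

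In section 9.8, report R0 over all treated, with patients who did not reach surgery as not achieved, alongside the rate among those operated on.

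The cost is protocol wording, settled before results are known, and a slightly lower reported rate. At 20% loss, power is 88% with 25 treated and 20 operated on, against the stated 89%; it is 74% if the trial stops at 20 treated.
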